**reaching cycle 56:**

- Reason for end of study
- Physical examination: ECOG
- Magnesium levels
- Concomitant medications
- AE/SAE
- Skin toxicity, skin toxicity management
- Dermatology Life Quality Index (DLQI) questionnaire
- EORTC QLQ-C30

Approved

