**Study Interruption:**

Reason for study interruption:

- Skin toxicity related to anti-EGFR
- Disease progression- Patient decision
- Investigator decision
- Death

Information available for each subject on all variables will be reported by study site staff in the study-specific sponsor database. The original data source will be patient records, from routine follow-up of subjects.

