### 9.3.1 Exposure Assessment

Treatment adherence: The percentage of delayed cycles, the percentage of cycles administered with reduced doses, the number of administered cycles, the median treatment duration and the average relative dose intensity of anti EGFR drug will be reported.

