### 9.3.2 Outcome Assessment

HRQoL will be measured using the EORTC QLQ-C30 questionnaire. The EORTC QLQ-C30 includes 5 functional scales (physical, role, emotional, social, and cognitive functioning), 3 symptom scales (fatigue, pain, and nausea and vomiting), a global health status scale, and a number of single items assessing additional symptoms (dyspnea, sleep disturbances, constipation, and diarrhea), and perceived financial impact. For the majority of the EORTC QLQ-C30 items a 4-point Likert-type response scale is used. The only exception is the global health status/QoL scale in which a 7-point Likert-type scale is used. For ease of interpretation, all scales and individual item responses are linearly converted to a 0 to 100 scale. EORTC QLQ-C30 scores reported during the treatment will be also expressed as percentage of the scores reported at baseline.

Skin satisfaction will be measured using the Dermatology Life Quality Index (DLQI). The DLQI questionnaire includes 10 questions scored from 0 (not at all, not relevant, not answered) to 3 (very much). The DLQI score is calculated by summing the scores of each question resulting in a minimum of 0 and a maximum of 30. A higher score means an impairment of the quality of life. The DLQI score will also be expressed as a percentage of the maximum possible score of 30. DLQI scores reported during the treatment will be also expressed as percentage of the DLQI scores reported at baseline.

Tolerability: The toxicity rate, defined as the percentage of patients, relative to the total of enrolled subjects, experiencing a specific adverse event of any grade, according to National Cancer Institute Common Toxicity Criteria (NCI CTC-AE version 4.02 ), will be reported. Times to onset of dermatological toxicities will be also described.

Treatment adherence: The percentage of delayed cycles, the percentage of cycles administered with reduced doses, the number of administered cycles, the median treatment duration and the average relative dose intensity of every planned drug will be reported.

Management of dermatological toxicity: concomitant medications, both topical and systemic, adopted to prevent or treat dermatological adverse events will be recorded.

Approved

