**9.7.2 Planned Method of Analysis**

**Outcome Variable(s):**

- HRQoL will be measured using the EORTC QLQ-C30 questionnaire. EORTC QLQ-C30 scores reported during the treatment will be also expressed as percentage of the scores reported at baseline.
- Skin satisfaction will be measured using the DLQI. The DLQI score will also be expressed as a percentage of the maximum possible score of 30. DLQI scores reported during the treatment will be also expressed as percentage of the DLQI scores reported at baseline.

Approved

- Tolerability: The toxicity rate, defined as the percentage of patients, relative to the total of enrolled subjects, experiencing a specific adverse event of any grade, according to National Cancer Institute Common Toxicity Criteria (NCI CTC-AE version 4.0), will be reported. Times to onset of dermatological toxicities will be also described.
- Management of dermatological toxicity: concomitant medications, both topical and systemic, adopted to prevent or treat dermatological adverse events will be recorded.

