### **Exposure Variable(s)**

Treatment adherence: The percentage of delayed cycles, the percentage of cycles administered with reduced doses, the number of administered cycles, the median treatment duration and the average relative dose intensity of every planned drug will be reported.

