#### **9.7.2.4 Analysis of the Primary, Secondary, and Exploratory Endpoint(s)**

To reach the primary endpoint ("To assess the impact of the treatment with FOLFOX or FOLFIRI plus anti-EGFR MAbs on patients' health related quality of life"), comparison between the QoL scores (total and partials) at different times will be done and

differences in mean from basal and follow-up times will be tested with T-test (Student T-test) paired data.

EORTC-QLQ C30 score will be calculated in the total population and also in the two subgroups: FOLFOX/FOLFIRI plus panitumumab and FOLFOX/FOLFIRI plus cetuximab.

Differences in mean between the two subpopulation will be tested at different times with T-test.

- To investigate the impact of dermatological adverse events during the treatment with FOLFOX or FOLFIRI plus anti-EGFR MABs on patients' skin satisfaction will be calculated the Dermatology Life Quality Index (DLQI) score.

Differences in mean between the two subpopulation will be tested at different times with T-test.

- To assess the tolerability of administered treatments, Tolerability and compliance to treatments will be described. Their effect on QoL will be evaluated with a multivariate analysis (Anova).
- To describe the adherence to the treatment **with antiEGFR** in terms of dose delays, dose reductions, number of administered cycles, average relative dose intensity of every drug, all these parameters will be described and the single values observed will be compared with the values reported previously, to determine variations .
- Every adverse event occurred will be described with particular attention to dermatologic ones: description, severity and management of the event will be illustrated. Correlation with number of event and treatments (FOLFOX/FOLFIRI plus panitumumab and FOLFOX/FOLFIRI plus cetuximab) will be verify with a multivariate analysis (Anova)
- Will be verified the presence of preemptive treatment of skin toxicities, and events of skin toxicities . The correlation between events of skin toxicities, QoL and presence of preemptive treatment will be tested with a multivariate analysis (Logistic)

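### The ANOVA of tolerability and compliance on QoL fixes neither outcome, factors nor exposure window; with cumulative factors such as number of cycles or ever having an event, it can show a spurious or sign-reversed effect

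*Combined protocol and SAP*

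**What the plan says.** Section 9.7.2.4, under the tolerability objective, first promises a description of tolerability and compliance and then adds: "Their effect on QoL will be evaluated with a multivariate analysis (Anova". The abstract repeats this. Neither place names the QoL value to be analysed, the factors, their coding or the period over which they are counted.

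The measures available as factors are listed elsewhere:

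- **Tolerability** (Sections 9.3.2 and 9.7.2): "The toxicity rate, defined as the percentage of patients, relative to the total of enrolled subjects, experiencing a specific adverse event of any grade". This is an ever/never count over whatever period each patient was observed.
- **Adherence, time-dependent part** (Sections 9.3.1 and 9.7.2): "the number of administered cycles, the median treatment duration".
- **Adherence, ratio part** (same sections): "The percentage of delayed cycles, the percentage of cycles administered with reduced doses", and relative dose intensity.
- **Number of events** is used in a separate ANOVA against treatment group in Section 9.7.2.4.

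Under Section 9.3, observation ends with anti-EGFR treatment, at withdrawal or on "reaching cycle 56". The listed reasons for interruption start with "Skin toxicity related to anti-EGFR" and go on to progression, patient or investigator decision, and death.

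Covariate assessment (9.3.3) and sensitivity analysis for residual confounding and bias (9.7.2.5.3) are marked not applicable. Missing data are not imputed (9.7.2.2).

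**The concern.** Ever having an event, event count, number of cycles and duration are known only when treatment ends, and all rise with time on treatment. If patients who feel better stay longer, they have higher on-treatment QoL, more cycles and more opportunity for events. An ANOVA of on-treatment QoL on these totals attributes that shared cause to the cycles or the events. It also explains QoL reported early by events that came later.

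This sentence is one of the places where the plan connects adverse events and adherence to the study's main outcome. A result in which patients with more adverse events appear to have better QoL would be reported as an effect, at the p < 0.05 level set in Section 9.7.2.1.

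A second risk is independent of the first. QoL is measured repeatedly, and plain ANOVA has no patient term. If every form becomes a row, forms from one patient are treated as independent.

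**Working it through.** **The plan's own figure.** The documents give no SD, effect size or power for this ANOVA. The relevant number is the expected questionnaire completers (Section 9.5): 0.50 × 300 = 150, as stated. I use n = 150 and n = 300.

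**Assumptions, not from the documents.** Between-patient QoL SD 15 and within-patient SD 15; treatment length lognormal with median 18 cycles, capped at 56; 0.3 events per cycle for everyone; no effect of cycles or events on QoL; correlation r between a patient's underlying QoL and treatment length; two-sided 5%.

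**Step 1: spurious gap by thirds of number of cycles.** The mean of the top third of a standard normal is 1.091, so the top-minus-bottom gap is 2 × 1.091 × r × 15.

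- r = 0.2: 6.5 points
- r = 0.1: 3.3 points

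**Step 2: false rejection rate.** With about 18 forms averaged per patient, the SD of a patient mean is √(225 + 225/18) = 15.4. The three group means lie at −d, 0 and +d, with d half the gap. The noncentrality is λ = n × (2d²/3)/15.4², referred to F(2, n−3).

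| r | n | λ | Rejection |
|---|---|---|---|
| 0.2 | 150 | 4.5 | 45% |
| 0.2 | 300 | 9.0 | 77% |
| 0.1 | 150 | 1.1 | 14% |
| 0.1 | 300 | 2.3 | 25% |
| 0 | either | 0 | 5% |

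Simulation of the same model agrees: 44–45% and 77–78% at r = 0.2. By thirds of event count, simulation gives 32–35% (n=150) and 61–62% (n=300) at r = 0.2, and 12% and 19% at r = 0.1.

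**Step 3: can the sign reverse?** A separate simulation at N = 300 used different assumptions: between-patient SD 16, within-patient SD 12, median about 8–13 cycles, and an event effect of 0 or −5 points from onset. The link in the left column is the QoL–duration correlation when the true effect is 0. Entries are the apparent difference in mean on-treatment QoL.

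| True effect | Link | Ever vs never event | High vs low event count |
|---|---|---|---|
| 0 | about 0.2 | +3.7 to +4.0 | +4.7 to +5.5 |
| 0 | about 0.37 | +7.5 to +7.8 | +9.0 to +9.9 |
| −5 | none | −2.8 to −3.9 | −1.7 to −2.8 |
| −5 | about 0.2 | −0.2 to +1.2 | +2.0 to +3.4 |
| −5 | about 0.37 | +3.7 to +4.8 | +6.4 to +8.0 |

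A real harm of 5 points is hidden or reversed once the link is present.

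**Step 4: choices that largely escape.** In the Step 1 model at r = 0.2:

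- Change from baseline: 4–6% rejection.
- QoL at a fixed visit by events before it: 4–5%.
- Share of delayed cycles: 7% and 9% at n = 150 and 300, gap 0.3 points.
- Events per cycle: 7–10%, gap about 0.4 points.

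If treatment length tracks the on-treatment change in QoL, change from baseline is affected again: 18% and 32% by cycles, 13% and 22% by event count.

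**Step 5: forms as independent rows.** With 12 forms per patient and within-patient correlation ρ (both assumed), the design effect for a patient-level factor is 1 + 11ρ. This is 5.4 at ρ = 0.4 and 7.6 at ρ = 0.6. The true rejection rate of a nominal 5% test is 2 × [1 − Φ(1.96/√design effect)]: 1.96/2.32 = 0.84 gives 40%, and 1.96/2.76 = 0.71 gives 48%.

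**The case against.** The strongest reply is that the plan never says these totals are the ANOVA factors. The toxicity rate is a cohort percentage to be reported, and median duration is a cohort statistic. A reader might infer that any ANOVA written under this sentence is biased. The documents do not support that, because the sentence leaves outcome, factors and window open and Step 4 shows ordinary choices that are nearly clean. Change from baseline is a natural one here: the plan also expresses QLQ-C30 scores as a percentage of baseline and tests differences from baseline. This part of the reply stands, and it makes the point conditional. It does not remove the point, because nothing in the plan steers the analyst to the safe choices, and the cumulative measures are among those listed.

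It also stands that ratio measures do not grow with time; that no QoL–duration correlation is documented; and that longer-treated patients with higher QoL would be a true association, so part of the fault lies in calling it an effect. The pooled-forms problem is likewise conditional: no section says forms will be pooled.

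The statement in Section 7.3 that analyses are descriptive only helps less. Section 9.7.2.1 sets a significance level, Section 9.7.2.4 speaks of an effect, and a reversed estimate misleads with or without a p-value.

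Finally, this is an analysis under a secondary objective. A reader might infer that the primary result is compromised; the paired t-tests do not use these factors and are not touched by this point.

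**Conclusion.** The concern holds conditionally. The plan commits to an ANOVA for an effect on repeatedly measured QoL and leaves open whether the factors are cumulative totals. If they are, and the outcome is on-treatment QoL, the result can be spurious or of the wrong sign. The size rests on the assumed link between QoL and treatment length: substantial at 0.2, modest at 0.1, absent at zero. The stopping reasons make some link plausible, but the documents do not quantify it. The sign reversal depends on the further assumptions in Step 3. Ignoring clustering would be a separate and comparably large error if forms were pooled. The plan should be changed, since a better method is available on data already collected.

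**What to change.** In Section 9.7.2.4 and the abstract, replace the ANOVA with a linear mixed model for the repeated QLQ-C30 scores:

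- a random patient effect, baseline score and cycle;
- adverse-event status and dose-modification status up to the previous assessment, as lagged time-varying covariates;
- within-patient and between-patient components separated, with the within-patient coefficient as the reported answer.

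State that number of cycles, duration, ever-event and event count will not be used as explanatory factors. If a patient-level summary is wanted, use per-cycle rates. Report the result as an association.

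In the Step 3 setting, a within-patient time-varying model returned 0.0 when the truth was 0 (3–6% rejection) and −4.9 to −5.0 when it was −5. That check used exposure from onset and patient-centred data; the full lagged mixed model was not itself simulated.

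Cost: SAP wording, moderate programming and a model less simple to present. Events and treatment modifications are recorded before every cycle, and QoL repeatedly, so no new data are needed. Section 9.1 gives the QoL schedule both as every other cycle and as every 2 weeks, so the lag should be defined by the previous assessment.

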## 9.2.3 Subject/Patient/Healthcare Professional Eligibility

### 9.2.3.1 Inclusion Criteria

Adult ( $\geq$  18 years old) RAS wild-type metastatic colorectal cancer patients candidate to receive FOLFOX or FOLFIRI plus panitumumab or FOLFOX or FOLFIRI plus cetuximab as upfront treatment as per clinical practice.

Willingness and ability to comply with the protocol.

Written informed consent to study procedures.

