### 11.2 Safety Collection, Recording and Submission to Amgen Requirements

**This study is prospectively collecting information of enrolled patients. All safety events (adverse events, product complaints, and other safety findings) considered to have occurred following subject exposure to anti-EGFR will be collected from signing of the informed consent form to the final study contact. The investigator is responsible for recording safety events that they become aware of during study period in the patient's appropriate documentation.**

**Collected safety events occurred after subject exposure to panitumumab, with the exception of the protocol-exempted events listed in the section below, must be**

**submitted as individual safety reports to Amgen via the applicable Amgen Safety Reporting Form (paper form) within 1 business day of investigator awareness.**

See [Appendix B](#) for sample Safety Report Form(s), [Appendix C](#) for Additional Safety Reporting Information regarding the adverse event grading scale used in this study, and [Appendix D](#) for sample Pregnancy and Lactation Notification Worksheets.

The Investigator may be asked to provide additional information for any event submitted, which may include a discharge summary or extracts from the medical record.

Information provided about the event must be consistent with information recorded **in the study documentation** where safety data may also be recorded (eg.: **Case Report Form, CRF**).

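### The adverse-event count comparison between panitumumab and cetuximab makes no allowance for time on treatment, and the toxicity rate divides by enrolled rather than exposed patients

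*Combined protocol and SAP*

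**What the plan says.** **Event counts.** Section 9.7.2.4 plans the comparison as follows: "Correlation with number of event and treatments (FOLFOX/FOLFIRI plus panitumumab and FOLFOX/FOLFIRI plus cetuximab) will be verify with a multivariate analysis (Anova". It names no covariate, offset or person-time. Covariate Assessment (9.3.3), the sensitivity analyses (9.7.2.5 and its subsections) and the analysis of safety endpoints (9.7.3) are all marked not applicable.

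**Observation time.** Section 9.1 has adverse events recorded before every cycle. Under the End Of Study Visit in Section 9.3, observation closes after anti-EGFR treatment ends, at withdrawal, or on "reaching cycle 56". Cycles administered and median treatment duration are reported, but only as adherence (9.3.1 and 9.7.2). The one time-related safety output is a description of time to onset, for dermatological toxicities only.

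**Toxicity rate.** Section 9.3.2 defines it thus: "The toxicity rate, defined as the percentage of patients, relative to the total of enrolled subjects, experiencing a specific adverse event of any grade". The Abstract and Section 9.7.2 repeat the definition. Eligibility in Section 9.2.3.1 covers "metastatic colorectal cancer patients candidate to receive FOLFOX or FOLFIRI plus panitumumab" or the cetuximab equivalent, so candidacy suffices and receipt of drug is not required. Section 11.2 collects events "considered to have occurred following subject exposure to anti-EGFR". No treated or safety population is defined.

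**The concern.** A patient's event count accumulates with time at risk. A comparison of raw counts therefore mixes two quantities: how often events occur per cycle, and how many cycles were given. Drug choice is the clinician's and is not randomised, so equal duration in the two groups cannot be presumed. If one drug is continued for longer, for whatever reason, its patients accumulate more events and the ANOVA can attribute the excess to the drug.

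The denominator is a second, separate matter. An enrolled patient who never receives an anti-EGFR dose counts in the denominator but cannot enter the numerator, so the rate can only be pulled down.

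Tolerability is a secondary objective (8.2), and Section 7 gives real-life adverse-event incidence as a reason for the study. Both problems touch figures that readers will want to use.

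**Working it through.** **The plan's own figure.** Section 9.5 expects 300 × 0.50 = 150 patients to complete the questionnaires. That reproduces, but it concerns questionnaire completion and does not bear on adverse events. The plan has no power or event-rate calculation to check.

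**1. Direction of the count bias.** Let r be the event rate per cycle, equal in both groups, and T the number of cycles. The expected count per patient is r × E(T), so the ratio of mean counts equals the ratio of mean durations. For 15 vs 12 cycles it is 15/12 = 1.25, and for 18 vs 12 it is 18/12 = 1.50 (before the cap at 56), although the drugs are equally toxic per cycle.

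**2. Size of the count bias.** Inputs from the documents: significance level 0.05 (9.7.2.1; two-sided is assumed because the plan does not say) and the cap at 56 cycles. Assumed inputs: 150 patients per group (an even split of 300; no split by drug is stated), 0.5 events per cycle, gamma frailty with variance 1, and exponential durations rounded up to whole cycles. False-positive rate of a one-way ANOVA on raw counts, as a range over repeated simulation runs:

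| Mean cycles | Raw-count ANOVA |
|---|---|
| 12 vs 12 | about 5% |
| 12 vs 15 | 17-19% |
| 12 vs 18 | 45-47% |

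A separate simulation with smaller frailty (coefficient of variation 0.5) and geometric durations shows the same pattern: 5.5% at 14 vs 14 cycles, 18.6% at 14 vs 12 and 62.0% at 14 vs 10. An exposure-adjusted rate-ratio test on the same data stayed between 5.3% and 6.6%.

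**3. Which adjustment is safe.** With a constant event rate, a negative binomial model with a log(cycles) offset holds its level at roughly 4-6%. To test that assumption, events were made front-loaded and identical for both drugs: 1.0 per cycle for the first 4 cycles, then 0.1 (assumed).

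| Mean cycles | Raw-count ANOVA | Negative binomial, log(cycles) offset |
|---|---|---|
| 12 vs 15 | 7.5% | about 13% |
| 12 vs 18 | 16% | about 25% |

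Nearly all the offset model's errors called the longer-treated drug less toxic. Adding number of cycles as a covariate to the linear model held 4-6% under both event patterns.

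**4. The crude percentage also depends on duration.** With risk h per cycle, the probability of at least one event in c cycles is 1 − (1 − h)^c. At h = 5% (assumed) this is 26.5% for c = 6, 46.0% for c = 12 and 94.3% for c = 56.

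**5. Denominator.** With u the never-treated share, reported rate = true rate among exposed × (1 − u). The true rates are the ends of the 50-90% range for cutaneous effects in Section 7; u is assumed.

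| u | Exposed of 300 | True 90% reported as | True 50% reported as |
|---|---|---|---|
| 1% | 297 | 0.90 × 0.99 = 89.1% | 0.50 × 0.99 = 49.5% |
| 2% | 294 | 0.90 × 0.98 = 88.2% | 0.50 × 0.98 = 49.0% |
| 10% | 270 | 0.90 × 0.90 = 81.0% | 0.50 × 0.90 = 45.0% |

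**The case against.** **No imbalance is documented.** The plan gives neither duration by drug nor a never-treated count. At equal durations the ANOVA holds its level, and at 12 vs 13 cycles its error is only 6.9%. This stands: the bias is conditional, and a reader who infers that the comparison will mislabel the longer-treated drug goes further than the documents allow.

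**Skewed counts.** A reader might infer that ANOVA is invalid because event counts are skewed. The check does not support that. At equal durations the error is about 5% on heavily skewed counts, and the same linear model with cycles added performs well. The missing exposure term is the defect, not the distributional family.

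**Descriptive intent.** Section 7.3 says that no inference is planned, the tolerability endpoint is a percentage rather than the ANOVA, and reported cycles and duration would let readers see an imbalance. This softens the consequence but does not remove it. Section 9.7.2.1 sets a significance level, Section 9.7.2.4 plans the test, and without any p-value the raw mean counts would still track duration.

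**A multivariate analysis could include exposure.** It could, but none is named and Covariate Assessment is marked not applicable, so the analyst has no instruction to include it.

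**Few patients will be never-treated.** Section 9.1 requires the prescribing decision to precede study entry, and the plan does not define enrolment. This stands: the denominator effect is probably small, and the documents do not support an inference that incidences are materially understated.

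**Conclusion.** The point holds in conditional form. As written, the count comparison leaves time on treatment out, so it is reliable only if the two drug groups are treated for similar lengths of time. Nothing in the plan ensures that. Under the stated assumptions, a gap of 12 vs 15 mean cycles raises the false-positive rate from about 5% to 17-19%, and 12 vs 18 raises it to 45-47%; when events cluster early the inflation is smaller. The error runs against the longer-treated drug.

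The denominator mismatch is a separate and probably minor point: about 1 to 2 percentage points on a true 90% if 1% to 2% of enrolled patients are never treated. Its direction is certain and its size is unknown.

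Both concern a secondary objective and should be corrected. Neither affects the primary quality-of-life analysis.

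**What to change.** **Section 9.7.2.4.** State how time on treatment enters the event-count comparison, and choose the method before the data are analysed. Any of these would serve:
- add number of administered cycles as a covariate to the planned model;
- use a count model with exposure in which the event rate may differ by period, such as early vs later cycles;
- compare the groups over a common early window.

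Do not rely on a constant-rate log(cycles) offset alone, because it can bias the comparison the other way if events cluster early. Cycles received may themselves reflect toxicity, since skin toxicity is a listed reason for interruption in Section 9.3, so the adjusted result should be described as an association.

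**Reporting.** Give events per patient-month or per cycle by drug beside the crude percentages.

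**Abstract, 9.3.2 and 9.7.2.** Define the toxicity-rate denominator as patients who received at least one anti-EGFR dose, and report the number enrolled but never treated.

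**Cost.** Wording and a little more analysis work. Administered treatment is already recorded at each study visit, so no new data are needed. Stated incidences will become slightly higher if any enrolled patients were never treated.
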